9. **CCI**

10. Patients at 1 clinical investigative site will undergo **CCI** during Screening and at the Week 24 Visit and Week 48 Visit (proptosis non-responders who elect to receive open-label TEPEZZA). The Week 24 **CCI** will not need to be performed on the same day as other Week 24 assessments as long as it is performed within the visit window and prior to the Week 24 infusion (proptosis non-responders who elect to receive open-label TEPEZZA). The Week 48 **CCI** will not need to be performed on the same day as other Week 48 assessments as long as it is performed within the visit window.

11. Clinical Activity Score must be <1 in both eyes at the Screening and Baseline Visits.

12. For women of childbearing potential (including those with an onset of menopause < 2 years prior to Screening, non-therapy-induced amenorrhea for < 12 months prior to Screening, or not surgically sterile [absence of ovaries and/or uterus]), a serum pregnancy test will be performed at Screening and urine pregnancy tests will be performed prior to dosing at all other visits, as applicable, and at the End-of-Treatment Visit.

13. Patients who have decreased best-corrected visual acuity due to optic neuropathy (defined by a decrease in vision of 2 lines on the Snellen chart, new visual field defect, or color defect secondary to optic nerve involvement within the last 6 months) are not eligible for randomization.

14. Vital signs (blood pressure, heart rate, respiratory rate, temperature) will be measured at all clinic visits. Vital signs will be measured pre- and post-infusion on Day 1 and Week 3 (all patients), pre- and post-infusion at Week 24 and Week 27 (proptosis non-responders who elect to receive open-label TEPEZZA) and pre-infusion on all other infusion days. Additional vital signs will be monitored if infusion-associated AEs occur (see Section 9.5.3.4 for details).

15. Patients must be euthyroid, with the Baseline disease under control or have mild hypo- or hyperthyroidism (defined as FT4 and FT3 levels < 50% above or below the normal limits). Every effort should be made to correct the mild hypo- or hyperthyroidism promptly and to maintain the euthyroid state for the full duration of the trial.

16. HbA1c must be < 8.0% to be eligible for the trial. If the HbA1c is elevated and considered clinically significant at any time point after Screening, it will be repeated approximately every 90 days until it returns to normal or Baseline value.

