### 9.3 Selection of Trial Population

#### 9.3.1 Inclusion Criteria

Eligible patients must meet provide all the following criteria:

1. Written informed consent.
2. Male or female at least 18 years old at Screening.
3. Initial diagnosis of TED ≥2 years but <10 years prior to Screening. Clinical diagnosis of stable, chronic (inactive) TED, as determined by patient medical records indicating a CAS ≤1 in both eyes for at least 1 year prior to Screening or all of the following:
  - a. no progression in proptosis for at least 1 year prior to Screening
  - b. if patient has history of diplopia due to TED, no progression in diplopia for at least 1 year prior to Screening
  - c. no new inflammatory TED symptoms for at least 1 year prior to Screening.
4. CAS ≤1 at the Screening and Baseline Visits.
5. Proptosis >3-mm increase from the patient's baseline (prior to diagnosis of TED), as estimated by treating physician and/or proptosis >3 mm above normal for race and gender.
6. Patients must be euthyroid with the patient's baseline disease under control or have mild hypo- or hyperthyroidism (defined as free thyroxine and free triiodothyronine levels <50% above or below the normal limits) at Screening. Every effort should be made to correct the mild hypo- or hyperthyroidism promptly and to maintain the euthyroid state for the full duration of the trial.
7. Does not require immediate surgical ophthalmological intervention and is not planning corrective surgery/irradiation during the course of the trial.
8. Diabetic patients must have HbA1c ≤8.0% at Screening.
9. Patients with a history of inflammatory bowel disease, ulcerative colitis or Crohn's disease must be in clinical remission for at least 3 months, with no history of bowel surgery within 6 months prior to screening and no planned surgery during the trial. Concomitant stable therapies for inflammatory bowel disease without modifications in the 3 months prior to Screening are allowed.

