#### **Risk of Hyperglycemia**

- In nonclinical studies, there was no *in vitro* cross-reactivity of teprotumumab with the insulin receptor. Clinical trials in Active TED have shown a higher incidence of hyperglycemia in patients treated with teprotumumab compared to placebo. Patients with pre-existing diabetes mellitus (who were under appropriate glycemic control upon trial entry) or impaired glucose tolerance were more likely to experience an event of hyperglycemia after exposure to teprotumumab.

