#### **Management of Patients with Diabetes Mellitus**

- Patients with known controlled diabetes mellitus are allowed to participate in trials with teprotumumab. HbA1c levels should be monitored every 6 weeks in these patients.
- Investigators are strongly encouraged to adjust their patients' diabetes management to maintain HbA1c levels ~8%. In the event a patient's HbA1c level rises to >8% while in the trial, the Investigator must assess the risk versus benefit for the patient to remain in the trial, discuss with sponsor's medical monitor or designee, and document the decision.

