- Perform efficacy assessments (proptosis, CCI [REDACTED]).
- Record vital signs prior to and at the end of the infusion. Additional vital sign monitoring may be performed in the event of infusion-associated AEs (see Section 9.5.3.4 for details).
- Obtain calculated trial drug dose, vial assignment (if applicable) and volume of trial drug to be administered from the EDC system.
- Administer trial drug and record date, volume and start/stop times of the infusion. Monitor the patient for any AEs during the infusion and for 60 minutes after the completion of the infusion.
- Collect post-dose blood samples for PK analyses following the end of the infusion.
- Enter visit data in the EDC system.

Patients will be discharged from the site after all procedures have been completed, instructed to return for a clinic visit in 3 weeks and contacted the following day to perform a safety check following the second infusion.

#### 9.5.6.2.3 Weeks 6, 12 and 18

- Collect predose urine sample for a pregnancy test for females of childbearing potential; the pregnancy test must be negative for the patient to receive trial drug.
- Obtain predose blood samples for hematology and fasting chemistry (including thyroid and HbA1c at Week 12 only).
- Inquire about AEs and concomitant medication use.
- Perform predose visual acuity assessment.
- Perform predose efficacy assessments (proptosis, **CCI** [REDACTED] and GO-QoL questionnaire [Weeks 6 and 12 only]).
- Perform predose CAS at Week 12 only.
- Record vital signs prior to the infusion. Additional vital sign monitoring may be performed in the event of infusion-associated AEs (see Section 9.5.3.4 for details).
- Collect predose blood samples for PK analysis, immunogenicity and **CCI** [REDACTED] at Week 12 only.
- Obtain calculated trial drug dose, vial assignment (if applicable) and volume of trial drug to be administered from the EDC system.
- Administer trial drug and record date, volume and start/stop times of the infusion. Monitor the patient for any AEs during the infusion and for 60 minutes (Week 6) or 30 minutes (Week 12 and Week 18) after the completion of the infusion.
- Collect post-dose blood samples for PK analyses following the end of the infusion at Week 12 only.
- Enter visit data in the EDC system.

Patients will be discharged from the site after all procedures have been completed and instructed to return for a clinic visit in 3 weeks.

#### 9.5.6.2.4 Weeks 9, 15 and 21

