#### 9.5.6.2.5 Week 24/End-of-Treatment 1/First Infusion of Open-label Treatment Period

Week 24 is the final visit of the double-masked Treatment Period. Trial drug is not administered for responders and non-responders who elect not to receive open-label TEPEZZA. For proptosis non-responders who elect to receive open-label TEPEZZA, the infusion will be performed at Week 24 (first of 8 infusions); all Week 24 procedures except AF and concomitant medication monitoring, post-infusion PK sample collection and 24-hour post-dose phone/email contact must be completed prior to TEPEZZA infusion.

- Perform efficacy assessments (proptosis, **CCI** [REDACTED] and GO-QoL questionnaire). The **CCI** will not need to be performed on the same day as other Week 24 assessments as long as it is performed within the visit window and prior to the first open-label infusion (proptosis non-responders who elect to receive open-label TEPEZZA).
- Perform CAS.
- Perform treatment response assessment, including whether the patient is a proptosis responder or non-responder, and enter data in EDC.

- Obtain blood samples for hematology and fasting chemistry (including thyroid and HbA1c) analysis.
- Collect urine sample for a pregnancy test for females of childbearing potential.
- Perform visual acuity assessment.
- Measure weight.
- Record vital signs (prior to and at the end of the infusion for non-responders who elect to receive open-label TEPEZZA). Additional vital sign monitoring may be performed in the event of infusion-associated AEs (see Section 9.5.3.4 for details).
- Collect blood samples for immunogenicity and **CCI** (NOTE: Collection should be prior to dose for non-responders who elect to receive open-label TEPEZZA.) Collect a single blood sample for PK analyses (proptosis responders and proptosis non-responders who elect not to receive open-label TEPEZZA). NOTE: **CCI**

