### 9.5.6.3 Open-label Treatment Period Visits After Week 24 – Proptosis Non-responders Who Choose to Receive Open-label TEPEZZA

Proptosis non-responders who elect to receive open-label TEPEZZA during the open-label Treatment Period will receive additional infusions at Weeks 27, 30, 33, 36, 39, 42 and 45.

#### 9.5.6.3.1 Week 27

- Collect predose urine sample for a pregnancy test for females of childbearing potential; the pregnancy test must be negative for the patient to receive TEPEZZA.
- Perform efficacy assessments (proptosis, **CCI**).
- Inquire about AEs and concomitant medication use.
- Collect blood samples for PK analyses prior to and at the end of the infusion.
- Collect predose blood sample for immunogenicity testing.
- Record vital signs prior to and at the end of the infusion. Additional vital sign monitoring may be performed in the event of infusion-associated AEs (see [Section 9.5.3.4](#) for details).
- Obtain calculated dose, vial assignment and volume of TEPEZZA to be administered from the EDC system.
- Administer TEPEZZA and record date, volume and start/stop times of the infusion. Monitor the patient for any AEs during the infusion and for 60 minutes after the completion of the infusion.
- Enter visit data in the EDC system.

Patients will be discharged from the site after all procedures have been completed, instructed to return for a clinic visit in 3 weeks and contacted the following day to perform a safety check following the second open-label infusion.

#### 9.5.6.3.2 Weeks 30, 36 and 42

- Collect predose urine sample for a pregnancy test for females of childbearing potential; the pregnancy test must be negative for the patient to receive TEPEZZA.
- Obtain predose blood samples for hematology and fasting chemistry (including thyroid and HbA1c at Week 36 only).
- Inquire about AEs and concomitant medication use.

- Perform predose visual acuity assessment.
- Perform predose efficacy assessments (proptosis, **CCI** [redacted] as well as GO-QoL questionnaire [Weeks 30 and 36 only]).
- Perform predose CAS at Week 36 only.
- Collect predose blood samples for PK analysis and immunogenicity testing at Week 36 only.
- Record vital signs prior to the infusion. Additional vital sign monitoring may be performed in the event of infusion-associated AEs (see [Section 9.5.3.4](#) for details).
- Obtain calculated dose, vial assignment and volume of TEPEZZA to be administered from the EDC system.

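### The protocol asks for HbA1c every 6 weeks in patients with known diabetes, but its schedule and visit lists draw it every 12 weeks

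*Protocol*

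**What the plan says.** Protocol 9.5.3.1.1.5, under management of patients with diabetes mellitus, admits patients with known controlled diabetes and says "HbA1c levels should be monitored every 6 weeks in these patients". If HbA1c rises above 8% during the trial, "the Investigator must assess the risk versus benefit for the patient to remain in the trial", discuss the case with the medical monitor or designee, and document the decision. Entry is permitted right up to that threshold: "Diabetic patients must have HbA1c ≤8.0% at Screening" (9.3.1). The same safety section states that patients with pre-existing diabetes or impaired glucose tolerance "were more likely to experience an event of hyperglycemia after exposure to teprotumumab".

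Section 9.5.3.7 refers to Section 2.1 for the timing of laboratory samples. The HbA1c row there, read with the visit lists in 9.5.6, gives Screening, Day 1 and Weeks 12, 24, 36 and 48. The list for Weeks 6, 12 and 18 reads "Obtain predose blood samples for hematology and fasting chemistry (including thyroid and HbA1c at Week 12 only". The list for Weeks 30, 36 and 42 reads "Obtain predose blood samples for hematology and fasting chemistry (including thyroid and HbA1c at Week 36 only". The Week 24 list reads "Obtain blood samples for hematology and fasting chemistry (including thyroid and HbA1c) analysis". The lists for Weeks 3, 9, 15 and 21 contain no HbA1c.

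The only other HbA1c rule in Section 2.1 is footnote 16. If a value after Screening is elevated and clinically significant, "it will be repeated approximately every 90 days until it returns to normal or Baseline value".

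**The concern.** Two instructions, both in the current protocol, set different HbA1c intervals for the same patients. The 6-week sentence came in with the Version 5.0 safety update. The table of changes for that version lists Sections 7.1.1, 7.1.2, 9.5.3.1.1.5 and 16, but neither 2.1 nor 9.5.6. The new safety text was therefore not carried into the pages that sites work from, and those pages restrict HbA1c to Week 12 and Week 36 among the 6-weekly laboratory visits.

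What is at stake is when the risk-benefit step can be triggered. The patients concerned may enter with HbA1c at the 8.0% limit, and the protocol itself names them as more likely to become hyperglycemic on this drug. Under the visit lists, the first scheduled HbA1c after a rise that follows the Week 12 sample is at Week 24, when masked dosing has ended.

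**Working it through.** No power or sample-size formula applies. The check is a count of visits and days.

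**Inputs.** Masked infusions are on Day 1 and Weeks 3, 6, 9, 12, 15, 18 and 21, and open-label infusions at Weeks 24, 27, 30, 33, 36, 39, 42 and 45 (Protocol 9.1). HbA1c draws are taken from the visit lists in 9.5.6, because the columns of the Section 2.1 table are shifted in the extracted text. Week w falls on Day 7w + 1, so Week 6 is Day 43, Week 12 Day 85, Week 18 Day 127, Week 21 Day 148 and Week 24 Day 169.

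**Checks after Baseline**

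| Period | Every 6 weeks (9.5.3.1.1.5) | Visit lists (9.5.6) |
|---|---|---|
| Masked dosing, to Week 21 | Weeks 6, 12, 18 = 3 | Week 12 = 1 |
| Masked period, to Week 24 | 4 | 2 |
| Open-label dosing, to Week 45 | Weeks 30, 36, 42 = 3 | Week 36 = 1 |
| All, to Week 48 | 8 | 4 |

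The shortfall in the masked period is two draws whether or not Week 24 is counted.

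**Infusions given before each predose sample**
- Week 6: 2 (Day 1, Week 3).
- Week 12: 4 (Day 1, Weeks 3, 6, 9).
- Week 18: 6.
- Week 24: 8.

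The first check therefore follows 4 infusions instead of 2. A rise just after the Week 12 sample meets its next scheduled check after 8 infusions (Week 24) instead of 6 (Week 18), assuming no infusion is withheld.

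**Longest gap between scheduled checks**
- Visit lists: 12 × 7 = 84 days, and 84 / 21 = 4 infusions.
- Every 6 weeks: 6 × 7 = 42 days, and 42 / 21 = 2 infusions.
- Worst-case extra delay: 84 − 42 = 42 days, or 4 − 2 = 2 infusions.

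**Does footnote 16 fill the gap?** It applies only after an elevated, clinically significant value.
- Elevated at Baseline: repeat at about Day 1 + 90 = Day 91, which is 6 days after the Week 12 target (Day 85).
- Elevated at Week 12: repeat at about Day 85 + 90 = Day 175, which is 6 days after the Week 24 target (Day 169) and after the last masked infusion (Day 148).

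Neither repeat gives a check near Week 6 (Day 43) or Week 18 (Day 127). The 90-day interval (90 / 7 = 12.9 weeks) is itself longer than 6 weeks.

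**The case against.** The strongest reply concedes the mismatch and disputes its weight.

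- The 6-week sentence says should, not must, and sits in safety background written for teprotumumab trials in general. Nothing in Section 2.1 forbids an extra HbA1c, and the above-8% trigger is not limited to scheduled samples. This stands: a site that reads the whole protocol could order the tests unscheduled. But the visit lists expressly confine HbA1c to Week 12 and Week 36, and a site working from them would omit the others.
- Fasting chemistry is already drawn every 6 weeks. Recurrent fasting glucose above 126 mg/dL calls for an evaluation in which HbA1c is an example test, so a result could arrive before Week 24. Section 9.4.6.3.2 requires fasting glucose to return to mild or moderate severity before the next infusion and allows infusions to be skipped. Ketoacidosis or hyperosmolar state stops treatment. This also stands, and it limits the harm. The glucose route is nevertheless conditional on recurrence and leaves management to the investigator's discretion, so it does not replace a planned HbA1c.
- Counting only masked dosing gives the starker contrast. Through Week 24 it is 2 against 4. Both counts are correct.
- The numbers of diabetic patients and of visits falling under Version 5.0 are unknown. This is true, so the effect can be stated per patient but not for the trial.
- Changing the sentence to 12 weeks would also remove the conflict, and the clinical basis may lie in the Investigator's Brochure, which is not available here. That is a legitimate alternative, but it would undo a recent safety instruction.

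**Conclusion.** The concern holds. The schedule and visit lists provide HbA1c at half the frequency that the protocol's own safety section asks for in patients with known diabetes, and footnote 16 does not make up the difference. For a diabetic patient followed by the visit lists, the worst case is a risk-benefit assessment delayed by 42 days or 2 infusions, possibly until masked dosing is over. Patients who enter the open-label period have the same pattern.

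This rests on the site following the visit lists, no infusion being withheld, and no HbA1c being prompted by a glucose finding. The consequence is a late assessment, not unwatched hyperglycemia, and no efficacy endpoint is touched. It should be corrected because it concerns a safety interval in patients the protocol identifies as being at higher risk, and because correction is cheap.

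**What to change.** 1. In Protocol 2.1, 9.5.6.2.3 and 9.5.6.3.2, add HbA1c for patients with known diabetes at Weeks 6 and 18, and at Weeks 30 and 42 for those in the open-label period.
2. In footnote 16, state that the 90-day repeat does not lengthen the 6-week interval for these patients.
3. In SAP 10.2, limit the all-patient HbA1c summaries and plot to Baseline and Weeks 12, 24, 36 and 48, and give the extra values in a listing only. Without this, the plot at the added visits would show diabetic patients alone. Because SAP 5.4.3 assigns every observation, including unscheduled ones, to an analysis visit, say explicitly that the extra values are not to be windowed into Weeks 12, 24, 36 or 48.
4. Update the copy of the schedule in SAP 15.1, which is based on the preceding protocol version, to conform.

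If the sponsor decides that 12 weeks is adequate, the alternative is to amend the sentence in 9.5.3.1.1.5. Adding the draws is preferred because the 6-week text is the newer safety instruction.

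The cost is protocol and SAP wording plus one extra tube at 2 visits per diabetic patient in the masked period, and at 2 more for those who enter the open-label period. Hematology and chemistry are already drawn at all four visits, so no visit is added.

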#### **Management of Hyperglycemia**

- Fasting glucose levels should be tested at Baseline. Random non-fasting glucose levels should be monitored at a minimum as per visit schedule.

- Patients with recurrent hyperglycemia, defined as a fasting glucose >126 mg/dL, will require evaluation for diabetes mellitus (e.g., fasting glucose, glucose tolerance and HbA1c tests) and appropriate medical management, at the discretion of the Investigator.

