Increase in blood glucose is a known AE observed in previous clinical trials with TEPEZZA and other IGF-1R antagonists and is known to respond to treatment. Since a referral for treatment of hyperglycemia may take some time, if the Investigator considers it appropriate to continue the

patient in the trial, the next scheduled infusion visit may be skipped to allow modified anti-diabetic treatment to take effect and hyperglycemia to return to mild/moderate level before dosing. The patient would then be dosed at the next scheduled visit (i.e., 6 weeks after the previous infusion). Fasting blood glucose levels must return to mild/moderate severity before the next scheduled infusion. The above process of withholding a scheduled infusion is recommended to occur at most twice during the trial for a single patient, after which dosing should continue only if the benefit of receiving continued treatment clearly outweighs the risk.

Any changes to the scheduled dosing interval (q3W) or adjustments in the infusion rate should be reported to the Sponsor/CRO.

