#### **9.5.3.7 Clinical Laboratory Safety Tests**

With the exception of urine pregnancy tests, a central laboratory will be used for all protocol-specified clinical laboratory parameters. Details of timing concerning the collection of these samples are presented in Section 2.1.

Instructions for the collection, handling and analysis of clinical laboratory samples will be provided to the site prior to site initiation.

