#### 9.6.1.4 Safety and Tolerability Endpoints

1. The incidence of TEAEs, SAFs, TEAEs resulting in premature discontinuation of treatment and AFSIs (infusion reactions, hyperglycemia, hearing impairment, new onset inflammatory bowel disease and exacerbation of inflammatory bowel disease).
2. The incidence of  $\geq$ Grade 3 TEAEs.
3. The change from Baseline to each scheduled visit in vital signs (blood pressure, heart rate, respiratory rate and temperature).
4. The results of best-corrected visual acuity.
5. The incidence of  $\geq$ Grade 3 fasting glucose values.
6. The change from Baseline to each scheduled visit in laboratory evaluations (hematology and fasting chemistry [including thyroid panel and HbA1c]).

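### The hyperglycemia text sends sites to the visit schedule for random non-fasting glucose after Baseline, but the schedule lists only fasting chemistry and a safety endpoint needs fasting values

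*Protocol*

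**What the plan says.** The instruction is in the current protocol (Version 5.0, Amendment 4.0), Section 9.5.3.1.1.5, under Management of Hyperglycemia: "Fasting glucose levels should be tested at Baseline. Random non-fasting glucose levels should be monitored at a minimum as per visit schedule". The Summary Table of Changes shows it as new text, brought in with an Investigator's Brochure update.

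The next bullet in the same place uses a fasting threshold: "Patients with recurrent hyperglycemia, defined as a fasting glucose >126 mg/dL".

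Section 9.5.3.7 says where laboratory timing is found: "Details of timing concerning the collection of these samples are presented in Section 2.1". The Schedule of Assessments there, and its copy in SAP Section 15.1, has a row for fasting chemistry and none for random or non-fasting glucose. The checklists in Section 9.5.6 agree. For Weeks 6, 12 and 18 they read "Obtain predose blood samples for hematology and fasting chemistry (including thyroid and HbA1c at Week 12 only"; for Week 24, "Obtain blood samples for hematology and fasting chemistry (including thyroid and HbA1c) analysis"; for Weeks 30, 36 and 42, "Obtain predose blood samples for hematology and fasting chemistry (including thyroid and HbA1c at Week 36 only". Week 48 has the same fasting-chemistry item as Week 24.

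Two other provisions call for a fasting value after Baseline. Section 9.4.6.3.2, on resuming after a skipped infusion, says "Fasting blood glucose levels must return to mild/moderate severity before the next scheduled infusion". Section 9.6.1.4 and SAP Section 3.2.4 make the incidence of Grade 3 or higher values a safety endpoint, in the words "Grade 3 fasting glucose values".

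**The concern.** The sentence ties fasting to Baseline only, changes to random non-fasting glucose for monitoring, and refers the site to a schedule in which every chemistry sample is a fasting one. The two texts give different fasting states for the same visits, and one predose sample cannot be both.

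Hyperglycemia is an adverse event of special interest. Section 7.1.2 singles it out as the one expected mechanism-related adverse event clearly attributed to the drug in Phase 2. Section 9.5.3.1.1.5 also says that patients with diabetes or impaired glucose tolerance are more prone to it, and patients with controlled diabetes may enroll. If sites let patients eat before scheduled visits, the fasting-glucose endpoint loses values in the area where the drug's safety profile most needs them, and the fasting rules for managing the patient cannot be applied to the sample in hand.

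**Working it through.** The plan states no figure on this point, so the check is a count and a comparison of texts.

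**Step 1. Count the visits.** Weeks are taken from the checklists in Section 9.5.6, because the table columns in the text available to me are not reliably aligned.

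| Period | Post-baseline clinic visits | Fasting chemistry listed | Random glucose listed |
|---|---|---|---|
| Masked | Weeks 3, 6, 9, 12, 15, 18, 21, 24 (8) | Weeks 6, 12, 18, 24 (4) | 0 |
| Open-label, after Week 24 | Weeks 27, 30, 33, 36, 39, 42, 45, 48 (8) | Weeks 30, 36, 42, 48 (4) | 0 |
| Total | 8 + 8 = 16 | 4 + 4 = 8 | 0 |

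I assume that the fasting chemistry panel contains glucose. The documents do not list the analytes, but no other scheduled item could supply the fasting-glucose endpoint.

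**Step 2. Read the sentence each way.**
- *As an addition:* random checks on top of scheduled fasting samples. The fasting values survive. But the stated minimum is whatever the schedule lists for random glucose, which is nothing at 16 of 16 visits, so the instruction has no content.
- *As a substitution:* fasting at Baseline, random afterwards at visits where glucose is drawn. Scheduled fasting values are then replaced.

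**Step 3. Bound the exposure per patient.** Under the additive reading, 0 values are lost. Under the substitutive reading, up to 4 are lost in the masked period and, for a patient who enters the open-label period, up to 4 more, or 4 + 4 = 8. The upper bound requires that all of the patient's visits fall after the 19 May 2023 amendment and that the site sets its checklist aside. The documents give neither the number of visits still to come at that date nor how sites read the text.

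**Step 4. See what each use of the value needs.**

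| Provision | Needs fasting? | Can an ad hoc fasting test supply it? |
|---|---|---|
| Grade 3 or higher endpoint (Protocol 9.6.1.4, SAP 3.2.4) | Yes | Not planned; it relies on scheduled samples |
| Definition of recurrent hyperglycemia (9.5.3.1.1.5) | Yes, stated | Yes; the same bullet lists fasting glucose in the work-up |
| Resuming after a skipped infusion (9.4.6.3.2) | Yes, stated | Yes, and often it must: no chemistry is listed at Weeks 3, 9, 15 or 21 |

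As an example of the last row, if the Week 12 infusion is skipped, dosing would resume at Week 15. The Week 15 checklist has no chemistry, so the site must order a separate fasting test whichever way it reads the sentence.

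**Step 5. Trace a non-fasting value through the SAP.** SAP Section 13 allows pooling of fasting and non-fasting records for chemistry other than glucose, so fasting status is evidently recorded and the other analytes are catered for. A non-fasting glucose would therefore most likely drop out of the fasting endpoint rather than be miscounted in it. Under the default denominator in SAP Section 5 (all patients in the group, including those with missing data), a lost value counts as no event unless the table shells say otherwise. Any effect on the reported incidence would then be downward.

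**The case against.** The strongest reply is that nothing replaces the fasting samples. The sentence sets a minimum and defers to the schedule, the schedule and every checklist say fasting, and nowhere does the text say that random glucose stands in for fasting glucose. A site works from its visit checklist, and such a site is unaffected.

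Most of this stands, and it limits the point to a conflict between instructions. It does not remove the conflict. The sentence contrasts fasting at Baseline with non-fasting monitoring afterwards, never says that the random checks are extra, and refers to a schedule that contains none. It is also the more recent text: the Summary Table of Changes shows no matching edit to Section 2.1 or to the checklists.

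A reader might infer that three protocol rules are compromised. The documents do not support that. The recurrent-hyperglycemia definition and the condition for resuming dosing each say fasting in their own words, and each can be met by a fasting test ordered for the purpose. Only the endpoint depends on the scheduled samples.

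A reader might also infer that SAP Section 10.2 needs correcting, because its graded shift table and its Grade 3 or higher table say only glucose. That is editorial. SAP Section 3.2.4 defines the endpoint on fasting values, Section 13 keeps glucose out of the pooling of fasting and non-fasting records, and Section 5.4.3 already puts all scheduled and unscheduled assessments in listings.

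**Conclusion.** The point holds as a conflicting instruction in current safety text. Section 9.5.3.1.1.5 asks for random non-fasting glucose on a schedule where fasting chemistry appears at 8 of 16 post-baseline visits and random glucose at none. A site that acts on the sentence at those visits would collect values that cannot serve the Grade 3 or higher fasting-glucose endpoint and cannot be applied directly to the two fasting management rules.

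It would go too far to conclude that fasting data will be missing. The loss lies between 0 and 4 scheduled values per patient in the masked period and between 0 and 4 in the open-label period, and nothing in the documents locates it within that range. The conclusion rests on two assumptions: that the fasting chemistry panel is the source of the glucose values, and that at least some sites might follow the amended sentence over the checklist.

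The consequence is confined to hyperglycemia management and to safety summaries that SAP Section 10 presents without hypothesis tests. The primary efficacy analysis is untouched. The correction is worth making because it is small and protects a named endpoint.

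**What to change.** In Protocol Section 9.5.3.1.1.5, Management of Hyperglycemia, replace the two sentences with: *Fasting glucose will be tested at Baseline and at every scheduled fasting-chemistry visit. Random glucose may be taken in addition and does not replace a scheduled fasting value.*

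This keeps any extra random checks that the sponsor may have intended and matches the schedule as it stands. Section 9.4.6.3.2, the Schedule of Assessments, the checklists and the SAP stay as they are. The cost is two replaced sentences in the next amendment and a note to sites, with no new visit or sample.
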